4.6.6 ECG

Actual values and change from baseline values will be summarized at each time-point using descriptive statistics for the following parameters: PR duration, QT duration, QRS duration, RR duration, QTc (Bazett) [QTcB], QTc (Fridericia) [QTcF].

ECG data will also be listed for patients with values outside the normal ranges and for patients with an ECG finding. The normal ranges will be based on the age of the patient at the time of the assessment. In addition, shift tables for each parameter (PR duration, QT duration, QRS duration, RR duration, QTcB, QTcF, T-wave, U-wave, sinus rhythm and overall interpretation) to compare the status at baseline to each time-point post-baseline and overall will be presented. The following normal ranges will be used:

Age (months)	PR Duration (ms)	QT Duration (ms)	QRS Duration (ms)	RR Duration (ms)	QTcF (ms)	QTcB (ms)
>24 and ≤144	80-160	260-390	40-90		380-450	300-450
>144	120-200	200-500	80-120	600-1500	380-450	300-450
>72 and ≤96				450-1000		
>96 and ≤144				600-1090		

The number and percentage of patients with an ECG finding at each time-point, (including the following atrioventricular [AV] blocks: 1st degree AV block, 2nd degree AV

block type I [Mobitz I], 2nd degree AV block type II [Mobitz II] and 3rd degree AV block), will also be summarized.

The number and percentage of patients with PR duration, QRS duration, QTcB and QTcF in the following ranges at each time-point will be presented:

ECG Parameter	Raw Value	Increase from Baseline
PR duration (ms)		
>24 and ≤144 months	≤ 160 > 160	
>144 months	≤ 200 > 200	
QRS duration (ms)		
>24 and ≤144 months	≤ 90 > 90	
>144 months	≤ 120 > 120	
QTcB (ms)		
	≤ 450	≤ 30
	> 450 and ≤ 480	> 30 and ≤ 60
	> 480 and ≤ 500	> 60
	> 500	
QTcF (ms)		
	≤ 450	≤ 30
	> 450 and ≤ 480	> 30 and ≤ 60
	> 480 and ≤ 500	> 60
	> 500	

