## LIST OF ABBREVIATIONS AND DEFINITIONS OF TERMS

Abbreviation	Definition
ALP	alkaline phosphatase
ALT	alanine aminotransferase
AST	aspartate aminotransferase
AUC 0-24	Area under the plasma concentration curve from administration to 24 hours
AUC 0-∞	area under the concentration-time curve from Time 0 to infinity
BID	twice a day
BMI	body mass index
BP	blood pressure
Caverage	average trough concentration
CGI-C	Clinical Global Impression of Change
CL/F	apparent clearance
Cmax	maximum concentration observed
EC	Ethics Committee
ECG	electrocardiogram
eCRF	electronic Case Report Form
EDC	electronic data capture
EQ-5D-5L	EuroQol 5-Dimension, 5-Level Questionnaire
FDA	Food and Drug Administration
FFM	fat free mass
FM	fat mass
FMI	fat mass index
FVC	Forced Expiratory Vital Capacity
HDL	High-density lipoprotein
HFMS	Hammersmith Functional Motor Scale
HN	home nursing
ICH	International Council for Harmonisation
IMP	investigational medicinal product
IxRS	Interactive Voice/Web Response System
LDL	low-density lipoprotein
LPLV	last patient, last visit
MFM	Motor Function Measure
OFS	Olesoxime Fatigability Survey
PD	pharmacodynamics
PedsQL™	Pediatric Quality of Life Inventory™

PK	pharmacokinetic
PQ	PQ interval: duration in milliseconds from the beginning of P wave to onset of ventricular depolarization (Q and R)
PRO	patient-reported outcome
QD	once a day
QRS	QRS interval: duration in milliseconds of the QRS-complex
QT	QT interval: duration in milliseconds from the beginning of Q wave to the end of T wave
QTcF	QT interval corrected using Fridericia's formula
RCR	Roche Clinical Repository
SF-36v2	Short Form-36 Health Survey, Version 2
SMA	spinal muscular atrophy
SMAIS	SMA Independence Scale
SMN	survival motor neuron protein
$t_{1/2}$	plasma concentration half-life
ULN	upper limit of normal
VAS	visual analog scale
WPAI:CG	Work Productivity and Activity Impairment: Caregiver

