4.6 SAFETY ANALYSES

All safety variables will be summarized using descriptive statistics. Analyses will be based on the safety population.

Post-baseline safety assessments, including assessments performed at an unscheduled visit or at an early discontinuation visit, will be assigned to a scheduled study visit based on the following time windows:

Visit	Study Day	Time Window (in Study Days)
V2 (Week 13)	92	Day 2 – Day 137
V3 (Week 26)	183	Day 138 – Day 228
V4 (Week 39)	274	Day 229 – Day 319
V5 (Week 52)	365	Day 320 – Day 456
V6 (Week 78)	547	Day 457 – Day 638
V7 (Week 104)	729	Day 639 – Day 820
V8 (Week 130)	911	Day 821 – Day 1002
V9 (Week 156)	1093	Day 1003 – Day 1184
V10 (Week 182)	1275	Day 1185 – Day 1366
V11 (Week 208)	1457	Day 1367 – Day 1548
...		

These time windows will be used for all parameters, including those that were not scheduled to be collected at that visit. If multiple valid values for a variable are recorded in the same time window, the record closest to the scheduled study visit will be selected for summary of the data.

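### SAP 4.6.6 sets the lower normal limit for QTcF 80 ms above that for QTcB, so traces normal on the SAP's own QT, RR and QTcB ranges are classed low on QTcF

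*SAP*

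**What the plan says.** SAP 4.6.6 summarises actual values and change from baseline for the ECG intervals, including both corrected QT measures, "QTc (Bazett) [QTcB], QTc (Fridericia) [QTcF". The Protocol's list of abbreviations defines QTcF as the "QT interval corrected using Fridericia's formula".

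The normal-range table in SAP 4.6.6 gives, in ms:

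| Age (months) | QT | RR | QTcF | QTcB |
|---|---|---|---|---|
| >24 to ≤144 | 260–390 | by sub-band below | 380–450 | 300–450 |
| >72 to ≤96 | – | 450–1000 | – | – |
| >96 to ≤144 | – | 600–1090 | – | – |
| >144 | 200–500 | 600–1500 | 380–450 | 300–450 |

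The ranges feed two outputs. One is a listing: "ECG data will also be listed for patients with values outside the normal ranges and for patients with an ECG finding". The other is a set of baseline-to-visit "shift tables for each parameter (PR duration, QT duration, QRS duration, RR duration, QTcB, QTcF, T-wave, U-wave, sinus rhythm and overall interpretation").

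A separate table in the same section counts patients by raw QTcB and QTcF (≤450, >450 to 480, >480 to 500, >500 ms) and by increase from baseline (≤30, >30 to 60, >60 ms). It uses the same cut-offs for both measures and has no lower limit.

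**The concern.** The two corrections are computed from the same QT and RR and are tied by a fixed relation. Their upper normal limits agree, but their lower limits differ by 80 ms. The difference also runs the wrong way: above 60 beats/min QTcF is the smaller number, yet it has to clear the higher floor. A trace that is unremarkable on every other range in the table can therefore be reported as abnormally low on QTcF.

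ECG parameters are part of the primary safety objective (Protocol 2.1), and Protocol 1.4 cites arrhythmias in dogs as the reason for extra cardiac monitoring. A floor placed among plausible values fills the QTcF listing with entries that are not findings. It also puts some patients in a low baseline row, so that chance movement across 380 ms reads as a change of status.

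**Working it through.** **Inputs.** The QT, RR, QTcF and QTcB ranges are those of SAP 4.6.6. The documents name the two corrections but do not write them out. The standard definitions, with RR in seconds, are:

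- QTcF = QT / RR^(1/3)
- QTcB = QT / RR^(1/2)
- hence QTcF = QTcB × RR^(1/6)

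The plan states no derived figure to reproduce. This is a consistency check of its table.

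**Step 1: what each floor means on the other scale.**

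| RR (ms) | Rate (/min) | QTcB when QTcF = 380 | QTcF when QTcB = 300 |
|---|---|---|---|
| 600 | 100 | 414 | 276 |
| 700 | 86 | 403 | 283 |
| 800 | 75 | 394 | 289 |
| 1000 | 60 | 380 | 300 |
| 1200 | 50 | 369 | 309 |
| 1500 | 40 | 355 | 321 |

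At 60/min the measures coincide, so any value from 300 to 379 ms is normal as QTcB and low as QTcF. At 100/min every QTcB below 414 ms is low on QTcF. Slow rates do not rescue the table. For both floors to describe the same trace, RR^(1/6) must equal 380/300, so RR = (380/300)^6 = 4.13 s, or 60/4.13 = 14.5 beats/min. That is far outside the SAP's RR ranges.

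**Step 2: a trace inside every other range.** Take QT 340 and RR 750 (80/min). QT is normal in both age rows and RR is normal in all three bands that have an RR range.

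- QTcB = 340 / 0.750^(1/2) = 393, normal
- QTcF = 340 / 0.750^(1/3) = 374, low

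**Step 3: the extreme of one band.** At >96 to 144 months, the highest normal QT (390) at the longest normal RR (1090) gives QTcF = 390 / 1.090^(1/3) = 379, already low. Above RR = (390/380)^3 = 1.081 s, no normal QT in that band can give a normal QTcF.

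**Step 4: how much of the table is affected.** On a uniform grid over the QT and RR ranges, keeping points with QTcB in 300–450, the part with QTcF below 380 is 72% (>72 to 96 months), 76% (>96 to 144) and 54% (>144). These are areas of the ranges, not patient frequencies, because QT and RR do not vary independently.

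**Step 5: patient frequency, by assumption only.** Under a normal model the share flagged low is Φ((380 − mean)/SD). None of these means, SDs or rates is in the documents.

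| Assumption | Share below 380 ms |
|---|---|
| QTcF mean 420, SD 15–25 | 0.4–6% |
| QTcF mean 410, SD 15–25 | 2–12% |
| QTcF mean 400, SD 15–25 | 9–21% |
| QTcF mean 390, SD 15–25 | 25–35% |
| QTcB mean 420, SD 20, 75/min (QTcF mean 405, SD 19.3) | 10% |
| QTcB mean 400, SD 20, 95/min (QTcF mean 370.5, SD 18.5) | 70% |

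For comparison, a 300 ms floor would flag less than 0.02% at QTcF means of 390–410 and SDs of 15–25.

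**Step 6: shifts with no drug effect.** With QTcF mean 400, total SD 15–25 and within-patient SD 8–12 (all assumed), about 10–16% of patients would cross 380 ms between two visits by chance. Fewer than 0.01% would cross 300 ms.

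**The case against.** The strongest reply is that little of consequence depends on this limit. "All safety variables will be summarized using descriptive statistics", and SAP 4.6.6 tracks QTcF prolongation in several ways that the floor cannot touch: actual values, change from baseline, counts above 450, 480 and 500 ms, and increases above 30 and 60 ms. This stands. A reader might infer that the floor would hide QT prolongation because a rise could show as a move from low to normal. The documents do not support that. The effect is limited to the low/normal boundary of one listing and one shift table.

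Second, no document gives a QTc distribution, so any single share of patients is borrowed from outside. This stands too. Nor should midpoints of the QT and RR ranges be read as typical traces, since QT moves with RR. The trace in Step 2 shows that the conflict exists, not how common it is.

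Third, the documents do not say which number is wrong. Elsewhere in SAP 4.6.6 QTcB comes before QTcF; only the normal-range table reverses them. Transposed column headings, in the SAP or in the reading of the PDF, are therefore possible, and a reader might wrongly conclude that 380 must be a typing error for 300. What is left is that, on the text as it reads, the two floors cannot be reconciled at any heart rate within the SAP's own ranges, and no reason is given.

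**Conclusion.** The table is wrong as written. Followed exactly, it puts false low entries in the QTcF out-of-range listing and makes chance movement across 380 ms look like a shift between low and normal. That conclusion rests only on the SAP's ranges and the definitions of the two corrections.

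Its reach is narrow, because detection of prolongation is intact. The number of patients affected cannot be derived: the assumptions tried run from under 1% to about 70%. I have taken the shift-table categories as low, normal and high, which the SAP does not spell out. With a two-way split the same traces would be misclassed as abnormal. The documents do not settle whether the cause is a wrong limit or swapped headings.

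**What to change.** Check the normal-range table in SAP 4.6.6, including the order of its QTcF and QTcB headings, against the ranges of the central ECG laboratory that assesses all tracings (Protocol 9.4). Then correct the lower limits so that the QTcF floor is not above the QTcB floor. Using the 300 ms already in the table for both is one example; another choice is acceptable if the laboratory's ranges support it. Leave the 450 ms upper limits, the >450/>480/>500 ms categories and the >30/>60 ms increase categories unchanged.

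The cost is a correction to a SAP table and the matching range in the programs. No data collection, visit or procedure changes.

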#### **4.4.8 Laboratory, Pharmacokinetic, Biomarker, and Other Biological Samples**

Laboratory safety tests will be collected at timepoints specified in the Schedule of Assessments ([Appendix 1](#)) and analyzed by a central laboratory. For safety monitoring purposes, the investigator must review, sign, and date all laboratory safety tests results.

Additional blood or urine samples may be taken at the discretion of the investigator if the results of any test falls outside the reference ranges, or clinical symptoms necessitate additional testing to monitor patient safety.

Samples for the following laboratory tests will be sent to one or several central laboratories for analysis:

- Hematology (WBC count, RBC count, hemoglobin, hematocrit, platelet count, differential count [neutrophils, eosinophils, basophils, monocytes, and lymphocytes])
- Blood chemistry: AST, ALT,  $\gamma$ -glutamyl transferase, creatine kinase, total and direct bilirubin, alkaline phosphatase (ALP), albumin, creatinine, urea, total protein, sodium, chloride, calcium, phosphorus, potassium, glucose, and additionally in adults and adolescents only, brain natriuretic peptide.
- Coagulation (INR, aPTT, PT).
- Lipids (cholesterol, low-density lipoprotein (LDL) cholesterol, high density lipoprotein (HDL) cholesterol, triglycerides)
- Urinalysis: a midstream, clean-catch urine specimen will be collected for dipstick analysis of protein, blood, glucose and pH. If there is a clinically significant positive result, urine will be sent to the laboratory for microscopy and culture. If there is an explanation for the positive dipstick result, it should be recorded, and there is no need to perform laboratory for microscopy and culture.
- Hormones

Patients aged 6-17 years: thyroid hormones (free thyroxine T4 and thyroid stimulating hormone).

Female patients aged 12-17 years or younger who have menses: estradiol, follicle stimulating hormone, luteinizing hormone.

- Pregnancy test

All women of childbearing potential ( $\leq$ 12 months of non-therapy-induced amenorrhea) or not surgically sterile will have urine pregnancy tests performed at all visits. If a urine pregnancy test is positive, it must be confirmed by a serum pregnancy test.

- Plasma samples for PK analysis

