4.6.4 Laboratory Data

Results of all laboratory tests collected will be summarized for each time-point using descriptive statistics for the actual values and change from baseline values.

Laboratory data will also be listed for patients with values outside the normal ranges (based on the central laboratory normal ranges), and shift tables to compare the status at baseline to each time-point post-baseline and overall will be presented. In addition, a plot of total bilirubin/upper limit of normal [ULN] versus alanine aminotransferase (ALT)/ULN and aspartate aminotransferase (AST)/ULN at each time-point will be presented.

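### The by-visit QTc category table and liver plot rest on one record per window chosen by closeness, and the SAP plans no any-time count for the higher QTc limits, QTc increases or the combined liver criterion

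*SAP*

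**What the plan says.** **Record selection (SAP 4.6).** "Post-baseline safety assessments, including assessments performed at an unscheduled visit or at an early discontinuation visit, will be assigned to a scheduled study visit" by day ranges. Where a window holds several valid values, "the record closest to the scheduled study visit will be selected for summary of the data". The section adds: "These time windows will be used for all parameters, including those that were not scheduled to be collected at that visit".

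**ECG (SAP 4.6.6).** "The number and percentage of patients with PR duration, QRS duration, QTcB and QTcF in the following ranges at each time-point will be presented". The QTcB and QTcF categories split at 450, 480 and 500 ms for the value and at 30 and 60 ms for the increase. PR and QRS have one age-dependent cut-off each and no increase category. The section also plans shift tables "to compare the status at baseline to each time-point post-baseline and overall will be presented", and a listing: "ECG data will also be listed for patients with values outside the normal ranges and for patients with an ECG finding".

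**Liver (SAP 4.6.4).** "a plot of total bilirubin/upper limit of normal [ULN] versus alanine aminotransferase (ALT)/ULN and aspartate aminotransferase (AST)/ULN at each time-point will be presented". Laboratory shift tables are by time-point and *overall*, and patients with out-of-range values are listed.

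**Unscheduled tests (Protocol 4.4.8).** "Additional blood or urine samples may be taken at the discretion of the investigator", when a result is out of range or symptoms call for it. Protocol 4.4.15 lets the patient's clinical needs decide what is done at an unscheduled visit.

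**The concern.** Choosing the record nearest the target day suits means and changes from baseline, because it keeps visits comparable and stops symptom-driven tests from distorting the average. It suits outlier displays poorly, because extra tests tend to be done when something is wrong, and the extreme value is what such a display exists to show.

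A by-visit display also does not say how many patients ever crossed a limit. The same few patients may recur from row to row, or different patients may appear each time, and the rows cannot tell these apart. A liver plot that pairs ALT and bilirubin at one visit can miss a bilirubin peak that comes after the ALT peak.

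Safety, including laboratory and ECG effects, is the primary objective (Protocol 2.1). The protocol cites arrhythmias and conduction abnormalities in dogs (1.4) and makes potential drug-induced liver injury an adverse event of special interest (5.2.3). There is no independent monitoring committee (SAP 3.2).

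**Working it through.** The plan states no figure for this point, so there is none to reproduce. Two checks apply.

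**1. How often would the closest-record rule displace an unscheduled test?**

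Inputs: windows and target days from SAP 4.6; visit windows from Protocol Appendix 1; ECGs at screening, V2 and then yearly (Appendix 1 notes), so V5, V7 and V9 within this range; safety laboratory tests at every visit.

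| Visit | Study days | Length | Target day | Visit window | ECG due |
|---|---|---|---|---|---|
| V2 | 2–137 | 136 | 92 | ±7 | yes |
| V3 | 138–228 | 91 | 183 | ±7 | no |
| V4 | 229–319 | 91 | 274 | ±7 | no |
| V5 | 320–456 | 137 | 365 | ±7 | yes |
| V6 | 457–638 | 182 | 547 | ±14 | no |
| V7 | 639–820 | 182 | 729 | ±14 | yes |
| V8 | 821–1002 | 182 | 911 | ±14 | no |
| V9 | 1003–1184 | 182 | 1093 | ±14 | yes |

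Total: 1183 days. Windows with a scheduled ECG: 136 + 137 + 182 + 182 = 637 days (53.8%).

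An unscheduled test is displaced if it lies further from the target day than the scheduled test. Two bounding assumptions are used: the scheduled test fell exactly on target (1 day per window is safe), or at the edge of its visit window (2 × 7 + 1 = 15 or 2 × 14 + 1 = 29 days are safe).

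- ECG, on target: (637 − 4)/1183 = 633/1183 = 53.5%.
- ECG, at the edge: (637 − 15 − 15 − 29 − 29)/1183 = 549/1183 = 46.4%.
- Laboratory, on target: (1183 − 8)/1183 = 1175/1183 = 99.3%.
- Laboratory, at the edge: (1183 − 4 × 15 − 4 × 29)/1183 = 1007/1183 = 85.1%.

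On the remaining ECG days, the unscheduled recording is usually the only one in its window and is kept.

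**2. Which any-time counts do the planned outputs give?**

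| Quantity | By-visit display | *Overall* shift table | Listing or AE route |
|---|---|---|---|
| PR above 160/200 ms, QRS above 90/120 ms, QTc above 450 ms | yes | possibly: same upper limits, *overall* undefined | listed, not counted |
| QTc above 480 or 500 ms | yes | no: normal-range status only | listed, not counted |
| QTc increase above 30 or 60 ms | yes | no | listed only if a value is out of range or there is an ECG finding |
| ALT/AST above 3 × ULN with bilirubin above 2 × ULN | plot, no count | no: one test at a time, normal limits only | reportable as an AE; no table for this criterion |

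An example for the third row: the QTcF normal range is 380 to 450 ms. A rise from 385 to 449 ms is +64 ms, in the SAP's own top increase category, yet both values are in range. If that record is displaced and there is no separate ECG finding, it need appear in no specified output.

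**The case against.** The case against a broader reading is strong, and most of it stands.

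- A reader might infer that no table shows how many patients ever crossed a limit. The SAP does not support that. Both sections plan *overall* shift tables, and the upper normal limits for PR, QRS and QTc equal the first cut-offs in the category table. For PR and QRS that is the only cut-off, so a properly defined *overall* shift table would already give the count.
- A reader might infer that an extreme found only at an unscheduled test never reaches a table. That is also too strong. The windows apply even where a parameter was not due, so an unscheduled ECG in the V3, V4, V6 or V8 window is normally alone and is counted. Displaced out-of-range values remain in the listings.
- A reader might try to put a figure on how far outlier rates are understated. The documents give no per-visit rate and no within-patient correlation. A per-visit rate and an any-time rate are also different quantities, and would differ without any unscheduled test.
- Protocol 5.3.5.6 makes combined liver cases reportable as adverse events within 24 hours, and AE tables use no visit windows. This protects against a case being lost but does not give the count. The most appropriate diagnosis is recorded, so cases may fall under different preferred terms, and the AE summaries in SAP 4.6.2 include no table for events of special interest.
- SAP 4.6.4 does not say that the selection rule governs the plot; that is read from the general rule. Even if the plot used all records, it would pair values by time-point and carry no count.
- By-visit display follows Protocol 6.6, and the study is descriptive. The change is an addition to a permissible plan rather than the correction of an error.

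**Conclusion.** The concern holds in a limited form. The outlier displays use one record per window, chosen by closeness, so a worst value at an unscheduled test can be left out. This is likely for laboratory tests (85% to 99% of days) and less so for ECGs (46% to 54%). These shares assume an unscheduled test on a random day and one scheduled test per due window, done on target or at the edge of its visit window. They say nothing about how many patients would be affected.

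Separately from displacement, no planned output counts patients who ever had QTc above 480 or 500 ms, a QTc increase above 30 or 60 ms, or the combined liver criterion. For PR, QRS, QTc 450 ms and the laboratory normal limits, the answer depends on what *overall* means. The SAP does not say whether it is the worst or last value, or whether it draws on all records or only the selected ones.

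This is a worthwhile, inexpensive improvement to the summary of the primary objective. The documents do not show that any reported rate would be wrong.

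**What to change.** 1. **SAP 4.6.6:** add a worst post-baseline row to the category table. Use each patient's maximum PR, QRS, QTcB and QTcF and, for QTcB and QTcF, the maximum increase, from all post-baseline records including unscheduled ones.
2. **SAP 4.6.4:** add a plot of each patient's peak ALT and peak AST (× ULN) against peak total bilirubin (× ULN), from all post-baseline records, with a count of patients above 3 × and 2 × ULN. Keep the by-visit plot. The two peaks need not coincide in time, so label this area as a screen and not as confirmed cases.
3. **SAP 4.6.4 and 4.6.6:** define *overall* in the shift tables as the worst post-baseline value over all records, with high and low directions kept apart where the range is two-sided.

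The closest-record rule can stay for means and changes from baseline. Display by dose is already required by Protocol 6.6 and needs no separate request.

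Cost: SAP wording and a few table or figure programs, using data already collected. Reported outlier rates may look less favourable, because an any-time proportion cannot be lower than the proportion at any single visit on the same denominator.
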